5. STUDY OUTCOMES

5.1 Primary Outcome

The primary outcome will be insomnia severity measured with the Insomnia Severity Index (ISI) (Bastien et al., 2001). The ISI will be administered before the intervention (T0) and one, two, 12, and 26 weeks after the start of the intervention.

5.2 Secondary Outcomes

The secondary outcome will be general mental health measured with the Brief Symptom Inventory (BSI) (Derogatis and Melisaratos, 1983). The BSI will be administered before the intervention (T0) and one, two, 12, and 26 weeks after the start of the intervention.

5.3 Exploratory Outcomes

Exploratory outcomes will be the severity of depressive symptoms (Beck Depression Inventory, BDI) (Beck et al., 1988), self-constructed visual analogue scales measuring mood, tiredness, concentration and subjective sleep quality, daytime sleepiness (Lapin et al., 2018), medication (self-reported) and hospitalization (self-reported number of inpatient stays within the follow-up period). Timepoints when the different exploratory outcomes will be administered can be found in table 1 (section 9.1).

5.4 Safety Outcomes

At T0, T1, T2, T3, and T4, participants will be asked about significant negative life events in order to assess possible adverse effects of the treatment. AEs will be categorized concerning the type of the reaction, severity, relatedness to the intervention, action taken and outcome (Raisch, Troutman, Sather, & Fudala, 2001).

6. STUDY DESIGN

6.1 General study design and justification of design

This project is a prospective randomized controlled clinical pilot trial with a cluster-crossover design

involving two groups: An interventional group (TAU, plus SleepExpert) and a control group (TAU plus sleep monitoring).

Two different wards in the trial site (UPD Bern) will constitute the clusters. The study is conceptualized with a crossover, i.e. clusters (wards) will first be randomized to one of the groups for a duration of 4 months. After a washout-phase of two months, they will then be allocated to the other group for another 4 months. The order (TAU plus SleepExpert first vs. TAU plus sleep monitoring first) will be randomly allocated in a 1:1 fashion.

A total of 60 patients will be included. Patients will be assessed before the intervention (T0) and at the following time-points after the start of the intervention: 1 week (T1), 2 weeks (T2), 12 weeks (T3) and 26 weeks (T4).

6.2 Methods of minimising bias

6.2.1 Randomization

Wards will be randomly assigned to one of the two treatment conditions (cluster-randomization). A random list will be generated via the website random.org.

Randomization, data acquisition, data entry, and data analysis will be performed by staff members that are blinded regarding the treatment condition.

6.2.2 Blinding procedures

Study participants and care providers cannot be blinded because they will notice whether they receive / deliver an actual treatment or a monitoring control. Due to the crossover cluster design (randomization of wards to either TAU plus sleep monitoring or TAU plus SleepExpert), patients who are on the same ward at the same time will not get in contact with patients who are in the other arm. Thus, contamination due to exchange between patients will be reduced as far as possible. There will be two different participant information sheets, one for patients in the SleepExpert group and one for patients in the control group. Patients in the control group will not be informed about the SleepExpert treatment program - they will only be informed about the sleep monitoring they will receive.

Outcome assessors (interviewers) and data analysts will be blinded. In the respective documents and database entries, patients will be identified with a code. The key for assigning the codes to patients will not be known to the interviewers and data analysts.

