7.3 Assignment to study groups

The two clusters (UPD wards) will be assigned to one of the following two study sequences – while one cluster will follow the first sequence, the other one will follow the second sequence. Which ward will follow which study sequence will be randomly assigned.

- TAU plus SleepExpert first for 4 months; fade-out for one month; wash-out for one month; TAU plus sleep monitoring for 4 months
- TAU plus sleep monitoring for 4 months; fade-out for one month, wash-out for one month; TAU plus SleepExpert for 4 months

During the TAU plus SleepExpert and TAU plus sleep monitoring phases, patients will be actively recruited. During the fade-out phases, no active recruitment will take place, but already recruited patients will be able to complete their treatment. During the wash-out phase, no recruitment and no study-related treatment will take place.

Depending at which stage of the study the ward stands at the time point when a subject is admitted to the ward, her or she will either receive TAU plus SleepExpert or TAU plus sleep monitoring, or, if admitted during the wash-out phase, the subject will not be able to participate in the trial.

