9.3.2 Timepoints T0 to T4

Time point T0 (day 0):

- Insomnia Severity Index
- Brief Symptom Inventory
- Beck Depression Inventory
- Visual analogue scales (subjective sleep quality, mood, concentration, and tiredness)
- Sleep diary will be handed out
- medication status
- adverse events

Time point T1 (day 7±2):

- Insomnia Severity Index
- Visual analogue scales (subjective sleep quality, mood, concentration, and tiredness)
- sleep diary will be checked
- medication status
- adverse events

Time point T2 (day 14±2):

- Insomnia Severity Index
- Brief Symptom Inventory
- Beck Depression Inventory
- Visual analogue scales (subjective sleep quality, mood, concentration, and tiredness)
- sleep diary will be checked
- medication status
- adverse events

Time point T3 (day 84±7):

- Insomnia Severity Index
- Visual analogue scales (subjective sleep quality, mood, concentration, and tiredness)

- sleep diary will be checked
- medication status
- adverse events

Time point T4 (day 182±7):

- Insomnia Severity Index
- Brief Symptom Inventory
- Beck Depression Inventory
- Visual analogue scales (subjective sleep quality, mood, concentration, and tiredness)
- sleep diary will be checked
- medication status
- adverse events

For details regarding the mentioned questionnaires, please see chapter 5.

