12.1.1 Case Report Forms

Data is recorded in paper CRFs as source documents. ECRFs will be given as an option for direct anonymized data entry from participants for follow-up time points when they are not patients on the wards anymore. The eCRFs will be created and stored on the database RedCap which is a database recommended from the Clinical Trial Unit Bern. Data entry from the source paper CRFs to eCRFs should only be performed by authorised personnel and data should be consistent with the available source documents. When this is not the case, a detailed explanation of the discrepancies should be provided. The principal investigator should ensure the accuracy, completeness, and timeliness of the data reported and sign off the completed eCRFs. In order to reflect the current patient status throughout the study, eCRFs will be kept up to date. This means that eCRFs should be completed no later than two weeks after a participant's visit and that data entry not should be delayed unnecessarily.

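### The patient code in 6.2.2 hides identity, not arm, so it cannot keep on-ward interviewers blinded (T0, T1, often T2), and the self-rated ISI is unblinded in any case

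*Combined protocol and SAP*

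**What the plan says.** Two sections claim blinding beyond the patient and the care provider.

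- Section 6.2.1: "Randomization, data acquisition, data entry, and data analysis will be performed by staff members that are blinded regarding the treatment condition".
- Section 6.2.2: "Outcome assessors (interviewers) and data analysts will be blinded". The means offered is coding: "The key for assigning the codes to patients will not be known to the interviewers and data analysts".

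The design sections fix how arm is assigned.

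- Section 6.1: "Two different wards in the trial site (UPD Bern) will constitute the clusters".
- Section 7.3: "while one cluster will follow the first sequence, the other one will follow the second sequence". A patient's arm follows from the ward's stage at admission: "Depending at which stage of the study the ward stands at the time point when a subject is admitted to the ward".

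Other sections bear on who can know the arm. Section 6.2.2 concedes that patients and care providers are not blinded, and 6.3 adds that ward staff always know whether their patients had SleepExpert. Sections 6.2.2 and 7.2 use a different information sheet in each arm. Section 3.6 says the control app gives no feedback or advice, unlike the SleepExpert version. Section 9.2.1 describes the ISI as a self-rating. For T1 to T4, section 9.3.2 lists "sleep diary will be checked" alongside the questionnaires and the adverse-event questions. Section 12.1.1 uses paper CRFs, with one alternative after discharge: "ECRFs will be given as an option for direct anonymized data entry from participants for follow-up time points".

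**The concern.** Blinding of the people who collect outcomes is listed among the methods of minimising bias, so a report that follows the protocol would repeat it. In this design the claim needs something that conceals a ward's current arm, and a patient code does not do that. With individual randomisation, each patient's arm could be concealed separately. Here a single remark by a nurse or patient reveals the arm of the whole ward for that phase.

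Two things are at stake. The first is how the primary result is described: a reader could take the ISI comparison as blinded assessment when it is not. The second is the data that interviewers can influence. These are the way questionnaires are administered on the ward, and the eliciting and rating of adverse events. Adverse events are categorised by severity and relatedness (5.4, 9.2.4.1) and compared between arms by chi-square test (safety analysis, section 11.4.4). The events foreseen in 10.3.1 include daytime sleepiness and a temporary worsening of sleep, where knowing the arm could affect both the asking and the rating.

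**Working it through.** The plan gives no figure on this point to reproduce. The check sets the design against the stated mechanism and lays out the calendar.

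**1. What determines arm.** Section 7.3 gives each ward 4 months of recruitment, 1 month of fade-out, 1 month of wash-out and 4 months of recruitment, with the wards in opposite order. Counted from the start, recruitment runs in months 0–4 and 6–10.

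| | Months 0–4 | Months 6–10 |
|---|---|---|
| Ward on sequence 1 | SleepExpert | Monitoring |
| Ward on sequence 2 | Monitoring | SleepExpert |

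2 wards × 2 phases = 4 cells, each with exactly one arm. Ward plus enrolment phase therefore gives the arm of 100% of patients to anyone who knows the sequence. The code key is not needed.

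**2. Which visits fall on the ward.** Section 8.1.1 gives a typical stay of 1 to 8 weeks (7 to 56 days). Assume, for illustration, that stays are uniform over that range. The share still admitted on day *d* after admission is (56 − *d*)/(56 − 7) for *d* between 7 and 56, and 0 beyond 56. The time from admission to T0 is not fixed beyond the 24 hours or more for consent, so two bounding cases are shown.

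| Visit | T0 at admission | T0 seven days after admission |
|---|---|---|
| T1 (day 7) | (56 − 7)/49 = 100% | (56 − 14)/49 = 86% |
| T2 (day 14) | (56 − 14)/49 = 86% | (56 − 21)/49 = 71% |
| T3 (day 84) | 0% | 0% |
| T4 (day 182) | 0% | 0% |

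On this assumption most patients are inpatients at T1 and T2, and nearly all have left by T3.

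**3. Late visits.** With 30.44 days per month, T4 falls 182/30.44 = 6.0 months after T0. Patients recruited in months 0–4 reach T4 in months 6–10, when their former ward is running the other arm. The visit date alone does not reveal arm at T4. Ward plus enrolment date still does.

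**4. Mechanism against need.** To mask an on-ward interviewer, the plan would have to conceal what the ward is running. The code conceals identity only. The ward's condition is known to all its staff (6.3) and appears in the consent documents (6.2.2, 7.2) and the app (3.6, 8.4).

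**5. The primary outcome.** The rater is the patient (9.2.1), and the patient is not blinded (6.2.2). Even perfect interviewer masking would not make the ISI a blinded assessment. The same holds for the BSI, the BDI and the visual analogue scales.

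**The case against.** The strongest reply is that the documents do not say who does what. Section 9.3.2 does not name the person who checks the diary. Nurses already discuss sleep behaviour and app use with SleepExpert patients (8.1.1), so it need not be the interviewer. The diary is handed out at T0, so a common form is not ruled out. No section places arm-aware staff beside a patient who is completing the ISI, and a paper CRF does not imply staff administration. Parts of section 1 were not available for this review, so silence on staffing should not be counted as a gap. An assessor based off the ward and kept from the phase calendar could stay masked. The protocol is also open about unblinded patients and care providers.

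Most of this stands, and it limits the point. A reader might infer that the blind must fail at every visit, that interviewers handle an arm-specific diary, or that the trial is open-label at every level of assessment. The documents do not support any of these:

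- The diary checker is unnamed.
- After discharge patients may enter data themselves (12.1.1), so masking at T3 and T4 is conceivable.
- Analysts see only pseudonyms (12.4). Although 11.4.2 gives the analysis to a principal investigator, nothing shows that analysts know the arm.

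The reply does not rescue the mechanism. The claim in 6.2.2 rests on the code, and the code does not conceal arm, whoever the interviewer is. Nor does openness about unblinded patients make interviewer blinding real.

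**Conclusion.** For assessments made on the ward, the stated blinding of interviewers and data collectors is not delivered by the mechanism described. This touches T0, T1 and often T2, that is, baseline and up to two of the four follow-up ISI scores, together with the adverse events asked about at those visits. At T3 and T4 masking is possible but not secured. The analyst claim is not shown to be wrong.

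The trial cannot report blinded assessment of the ISI, because the rater is an unblinded patient. That conclusion does not depend on staffing. Interviewer masking therefore bears mainly on questionnaire administration and on the eliciting and rating of adverse events.

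The one-arm-per-cell argument rests only on the design in 6.1 and 7.3. The inpatient shares rest on the assumed uniform stay and on the two assumed times from admission to T0. No bias in the ISI difference has been estimated, and sample size and primary model are unaffected. The change should be made because a bias safeguard would otherwise be reported without support.

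**What to change.** 1. In 6.2.1 and 6.2.2, withdraw the blinding claim for data acquisition and interviewers at on-ward visits. State that the ISI, BSI, BDI and visual analogue scales are self-reports by unblinded patients. Keep the analyst claim.
2. At T0–T2, have patients complete whichever of these questionnaires are scheduled themselves, before the diary check and the adverse-event questions. Use the direct REDCap entry of 12.1.1, or paper where a device or login is a problem.
3. Report adverse-event relatedness as unmasked. Mask the severity rating only where existing staff can do so without removing information needed to judge causality to the device (10.3, 10.3.2). Stripping app details from event descriptions would conflict with that assessment.

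**Cost.** Changed wording, a fixed order within the visit, and wider use of an existing form. Some inpatients may need a device or help: section 3.5 notes cognitive and motivational difficulties, and 8.8 relies on patients' own devices. A stated safeguard is given up for on-ward visits.

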6.2.3 Other methods of minimising bias

- The primary applicant is a staff member at the sleep clinic of the University Psychiatric Services Bern. The resources at this established, specialized sleep clinic will ensure that included patients are carefully diagnosed, i.e. that only patients fulfilling the defined eligibility criteria will be included. This ensures generalizability of the results to the intended population.
- Study attrition and reasons for dropout will be carefully documented throughout the study period.
- An intention to treat analysis will be provided since a per-protocol analysis may result in biased effects if many patients drop out due to (perceived) inefficacy.
- The outcome measures are widely used, valid, and reliable measures that have been recommended by experts for the research assessment of insomnia (Buysse, Ancoli-Israel, Edinger, Lichstein, & Morin, 2006).
- Therapists will be experienced, well-trained, and supervised.
- The trial will be registered in a publicly accessible database before recruitment of the first subject. Hypotheses and the analysis plan will be made publicly available. This precludes that the analysis plan is changed after inspection of the data ("fishing for significances").

6.3 Unblinding Procedures (Code break)

The code will only be broken if it is necessary in order to avert an immediate risk to the health of the person concerned or to guarantee the rights of the person or a legal basis exists for breaking the code. In this study, blinding of care providers and patients is not possible and will not be performed. Care providers on the wards will always be aware whether or not their patients received SleepExpert and data regarding the participation in the study intervention will be documented according to Good Clinical Practice. Thus, it is unlikely that circumstances under which the code has to be broken will occur.

7. STUDY POPULATION

7.1 Eligibility criteria

Minimal exclusion criteria will be defined with the aim of improving care for a broad population of patients with severe mental disorders and with the aim of maximizing generalizability and external validity.

Inclusion criteria:

- Age 18 years or older
- Documented diagnosis of acute insomnia, i.e. insomnia criteria according to ICD-10 for at least 2 weeks (Ellis et al., 2012)
- Insomnia Severity Index (ISI) total score > 7, equivalent to relevant insomnia (Gagnon et al., 2013)
- Inpatient in one of the two participating psychiatric wards in the UPD Bern
- Ability to understand the aims and procedures of the study
- Willingness to participate and ability to provide written informed consent

Exclusion criteria:

- Incapability of judgement
- Inability to participate in a low-threshold behavioral treatment program, e.g. due to severe cognitive impairment or high symptom severity precluding participation (e.g., severe catatonic symptoms, massive hallucinations, acute endangerment to self or others, involuntary commitment). Note that the named symptoms will lead to exclusion only if they lead to inability to give informed consent or an inability to participate in the program. Excluded patients will be re-assessed regularly and included if symptoms improve and participation is possible at a later point in time.

7.2 Recruitment and screening

During the enrolment phase, all patients admitted to the participating wards of the UPD Bern will be screened in person. The screening will consist of a few questions regarding sleep, implemented into the routine clinical interview at enrolment, and filling in the insomnia severity index (Gagnon et al., 2013). The clinical interview as well as the questionnaire (insomnia severity index) are part of the clinical routine in our hospital and not specific for this study. Eligible patients will be contacted by study staff, informed about the study, and invited to participate. For further information about the study a flyer containing the most important details will be given to the participants. The screening and enrolment process will be standardized across the wards to minimize the risk of selection bias.

Each patient in the clinic fills in a general consent form at admission, stating whether or not they agree to be approached for information about ongoing studies. Only patients who gave their written general consent will be contacted. There will be two different study information documents with attached consent forms, one for the active study phase where TAU plus SleepExpert is running, and one for the control phase where TAU plus sleep monitoring is running. Since patients are not randomized on an individual basis, but clusters (wards) are randomized, patients who are screened for the project in a phase where TAU plus sleep monitoring is running on their ward cannot be randomized to TAU plus SleepExpert. In these phases, it may be demotivating for patients to be informed about the SleepExpert treatment, because it is not available for them. Thus, we decided to give them extensive relevant information about the project they can participate in (sleep monitoring) and only basic information about the use of their data within a clinical trial.

7.3 Assignment to study groups

The two clusters (UPD wards) will be assigned to one of the following two study sequences – while one cluster will follow the first sequence, the other one will follow the second sequence. Which ward will follow which study sequence will be randomly assigned.

- TAU plus SleepExpert first for 4 months; fade-out for one month; wash-out for one month; TAU plus sleep monitoring for 4 months
- TAU plus sleep monitoring for 4 months; fade-out for one month, wash-out for one month; TAU plus SleepExpert for 4 months

During the TAU plus SleepExpert and TAU plus sleep monitoring phases, patients will be actively recruited. During the fade-out phases, no active recruitment will take place, but already recruited patients will be able to complete their treatment. During the wash-out phase, no recruitment and no study-related treatment will take place.

Depending at which stage of the study the ward stands at the time point when a subject is admitted to the ward, her or she will either receive TAU plus SleepExpert or TAU plus sleep monitoring, or, if admitted during the wash-out phase, the subject will not be able to participate in the trial.

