8.4 Compliance with study intervention

Adherence will be monitored using subjective patient data from the SleepExpert application. In the application, patients will log their bed times and rise times as well as subjective sleep times.

Treatment contamination (i.e., patients in the TAU plus sleep monitoring group learning about details of the SleepExpert intervention) will be prevented by cluster randomization of wards. One entire ward will be randomized to one of the conditions. The other ward will receive the remaining condition (preventing that both wards get the same condition). Patients in the control group will not get in close contact with patients in the intervention group. Additional measures to increase adherence include a start of the intervention in the inpatient setting along with individual coaching by nurses and a helpdesk that can be called in case of problems with the program. Please note that no further extensive contacts are planned to increase generalizability of the program after completion of the study.

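### Two wards of one hospital run opposite arms at the same time and the arm follows the ward, but the plan has no rule for ward placement or for patients who move between wards

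*Combined protocol and SAP*

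**What the plan says.** Section 6.1 sets the clusters: "Two different wards in the trial site (UPD Bern) will constitute the clusters". Section 7.3 puts them on opposite sequences ("while one cluster will follow the first sequence, the other one will follow the second sequence"), with recruiting phases of four months, and section 8.4 confirms that they never share an arm: "The other ward will receive the remaining condition (preventing that both wards get the same condition". Section 7.2 rules out allocation of individuals: "Since patients are not randomized on an individual basis, but clusters (wards) are randomized". What fixes a patient's arm is in section 7.3: "Depending at which stage of the study the ward stands at the time point when a subject is admitted to the ward", he or she gets whatever that ward is then running.

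The phases are open. Section 6.2.2 says that care providers cannot be blinded, and section 6.3 says: "Care providers on the wards will always be aware whether or not their patients received SleepExpert".

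The stated safeguard against selection is in section 7.2: "The screening and enrolment process will be standardized across the wards to minimize the risk of selection bias". By sections 7.2 and 9.3.1 it applies to patients already admitted to a study ward. The blinded staff in 6.2.1 randomise, collect, enter and analyse data; ward placement is not among their tasks. The other measures in 6.2.3 concern diagnosis, attrition, analysis set, instruments, therapists and registration.

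On separation of the arms, section 6.2.2 says that "patients who are on the same ward at the same time will not get in contact with patients who are in the other arm". No section covers a patient who changes ward. On the analysis set, section 6.2.3 promises intention to treat, while section 11.4.1 puts all analyses on an as-treated basis.

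**The concern.** The only random step is which ward starts with which arm. After that, being on one ward or the other decides the arm, and the safeguards start once the patient is already on a ward. If whoever places or moves patients has discretion and knows the phases, patients thought suited to a sleep programme could go more often to the ward running it.

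A cluster crossover protects against stable differences between wards. It does not protect against selection that changes wards when the arm changes, because that selection is inseparable from treatment. Baseline ISI in the primary model absorbs only what ISI carries; motivation, main diagnosis or expected length of stay could still differ.

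Transfers raise a more concrete problem. A patient moved to the other study ward is, on a plain reading of section 7.3, admitted to that ward in its current phase, and the as-treated set can then count the patient in the receiving arm. Section 6.2.3 points the other way. What is at stake is the efficacy contrast which, by section 11.2, informs whether a large confirmatory trial follows.

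**Working it through.** **1. The plan's own figure.** Section 11.2 gives N = 60 for d = 0.65, two-sided alpha 0.05, power 0.80. With 30 per arm (equal arms assumed), an exact two-sided t test has power 0.70 and would need 78 in total; 60 is reproduced only one-sided (power 0.80). That is a separate matter. Here d = 0.65 serves only as a yardstick.

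**2. What the crossover removes.** Let ward A run SleepExpert in period 1 and ward B in period 2. The arm contrast is

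½[(A1 − B1) + (B2 − A2)].

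- Stable ward difference w (A minus B): ½[w − w] = 0.
- Period effect: cancels within each bracket.
- Shift s among patients on whichever ward runs SleepExpert (in A1 and B2): ½[s + s] = s. Nothing is removed.

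A simulation agrees: 2 wards × 2 periods, 15 patients per cell, SD 1, no true effect, least squares with arm, ward and period terms, 20,000 runs per scenario. The assumed ward and period effects were 0.5 and 0.3 SD.

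| Arm-following shift (SD) | Bias (SD, absolute) | Two-sided false-positive rate |
|---|---|---|
| 0 | 0.00 | about 5% |
| 0.1 | 0.10 | 6.7% |
| 0.2 | 0.20 | 11.9% |
| 0.3 | 0.30 | 20.8% |

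The simulation includes a period term, which the primary model in section 11.4.2 does not list.

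**3. Illustrative size.** The documents give neither input, so both are assumed: a share f of an arm that is there through arm-following placement, and a gap δ = 0.5 SD between those patients and the rest, after adjustment for baseline ISI.

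- One arm affected: bias = f × δ, so 0.10 × 0.5 = 0.05 SD and 0.20 × 0.5 = 0.10 SD.
- Both arms sorted in opposite directions: bias = 2 × f × δ, so 0.10 SD and 0.20 SD. The two sorted groups then lie 2 × 0.5 = 1.0 SD apart.

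The false-positive rate is the chance that |T| exceeds the two-sided 5% limit, with T noncentral t on 58 degrees of freedom and noncentrality bias × √(30/2) = bias × 3.873.

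| Bias (SD) | Noncentrality | False-positive rate | Share of d = 0.65 |
|---|---|---|---|
| 0.05 | 0.19 | 5.4% | 8% |
| 0.10 | 0.39 | 6.7% | 15% |
| 0.20 | 0.77 | 11.9% | 31% |

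This treats patients as independent and ignores clustering and repeated ISI scores. The direction of any bias is not known.

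**4. A patient moved between the wards.** Section 7.3 ties the arm to admission to the ward, with no reference to an earlier stay on the other study ward. Section 11.4.1 analyses as treated. Section 6.2.3 promises intention to treat. Under the first two the patient can be counted in the receiving arm; under the third, in the arm of the first ward. The plan does not say which prevails.

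**The case against.** A reader might infer that whoever places patients knows the arm and in effect chooses it. The documents do not support that. They do not describe bed allocation at all, and sections 6.2.2 and 6.3 speak of care providers who deliver treatment on the wards, not of an admitting role. If catchment, diagnosis or another fixed rule unrelated to the arm decides the ward, the risk is small and any stable case-mix difference cancels. This stands, and it limits the point to an unaddressed risk.

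The plan also narrows the route. Study screening takes place after arrival on the ward, so no study eligibility result exists at first placement. Control patients are not told about SleepExpert, which limits requests from patients. Usual care is unchanged, and the programme adds a one-hour group session, about 2 × 5 = 10 minutes of nurse contact a week, and an app, so a motive to steer beds is itself an assumption. These points reduce the likelihood but do not close a clinician-driven route.

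For a patient moved after enrolment, intention to treat as promised in 6.2.3 would keep the arm of the first ward. That is right, but 11.4.1 says otherwise. Section 11.4 announces an analysis plan that will define analysis sets, and it could settle this; the present text does not. Mixing of patients from the two arms after a move is contamination, a different problem, and 6.2.2 claims only to reduce it as far as possible.

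Finally, this is a 60-patient pilot seeking experience and preliminary efficacy data. That lowers the priority, though the contrast still informs the decision on a confirmatory trial.

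**Conclusion.** The point holds as an uncontrolled risk. The structure is in the text: two wards of one site, always in opposite arms, arm set by ward and phase, phases open to care providers, and a selection safeguard that begins after ward arrival. It is also certain that selection following the arm would not cancel in the crossover. That such selection occurs is not shown.

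On the assumed inputs (10–20% of one arm, 0.5 SD gap, 30 per arm) the bias is 0.05–0.10 SD and the false-positive rate 5.4–6.7%, close to nominal. A reader might take 0.10–0.20 SD and 6.7–11.9% as the expected size; those figures require both arms to be sorted in opposite directions, which nothing in the documents indicates.

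The firmest part is the transfer rule: sections 7.3 and 11.4.1 together can assign a moved patient to the receiving arm, in conflict with 6.2.3. That can be repaired whatever the placement practice is. Overall this is an improvement to consider, not a required change.

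**What to change.** - **Section 7.3:** define a patient's arm by the first participating ward of the index admission, and state that a patient arriving by transfer from the other participating ward is not newly enrolled.
- **Section 11.4.1:** replace the as-treated set with analysis by that first ward, in line with 6.2.3.
- **As a check only:** record admission source (direct or transfer) on the screening log. By ward and phase, report counts of admissions, and compare baseline ISI and main diagnosis among enrolled patients. Limiting the patient-level comparison to enrolled patients avoids using study data from people who did not consent.

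These rules settle transfers. They do not prevent first placement from following the arm; the check could only make it visible. If ward placement follows a fixed rule, a sentence saying so would largely answer that part.

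The cost is a few sentences, one log field and the loss of any patients who arrive by transfer from the other ward. Their number is not given, and the loss sits somewhat against the aim in section 7.1 of minimal exclusions and of including patients later once they improve. Clinical placement is not changed.
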